12.7. Monitoring

The study will be monitored through local visits, telephone calls and periodic inspection of the CRD frequently enough to verify the following in monitored patients:

- Study Medication: storage conditions, that supplies are adequate throughout the clinical trial, that the Principal Investigators only administer the trial medication to patients included in the clinical trial, that the receipt, use and return of the study medication trial is adequately controlled and documented and that the disposal of unused medication complies with applicable regulatory requirements.
- Patient recruitment rate
- That written informed consent has been obtained prior to inclusion in the trial
- Compliance with approved protocol and amendments, if applicable
- That the researcher has the latest version of the Investigator's manual or the summary of product characteristics, all the supplies necessary for the correct development of the trial to comply with the applicable regulatory requirements.
- That the Investigator and his team are adequately informed about the trial
- Integrity and correctness of the data entered in the CRD, 100% SDV of the monitored patients
- CI/HIP: Signature/date and name of patient/investigator
- Eligibility criteria and selection tests
- Recording of adverse events, SAEs and SAE reports
- Main variable of the trial
- Dispensing/stock of IMP in the pharmacy service, traceability (brand, units, lot, etc.)
- Protocol deviations
- Collection, storage and shipping of biological samples/images
- Communicate deviations from the protocol, standard work procedures, good clinical practices and regulatory requirements applicable to the researcher and taking necessary actions to prevent the recurrence of detected deviations.

Monitoring visits will be carried out by the study monitors. It is understood that these monitors will be able to access the patients' medical records after requesting it from the researcher. The researcher will dedicate sufficient time to these visits and will facilitate access to all documentation to authorized persons.

The study may be audited by an independent body. Likewise, members of the CEIC of the Hospital where the trial is being carried out may make "follow-up visits" to it.

12.8. Amendments to the Protocol

Supplements or changes to the protocol can be made exclusively by the Promoter, who must send them to the Ethics Committee and the Regulatory Authorities (in Spain AEMPS) as amendments to the protocol.

12.9. Data processing

All data (personal, clinical, economic and from studies of biological material) obtained about patients will be processed in accordance with Regulation (EU) 2016/679 of the European Parliament and of the Council of April 27, 2016 regarding the protection of natural persons with regard to the processing of personal data and the free circulation of these data and repealing the European Parliament Directive 95/46/EC of October 24, 1995 on the protection of individuals with respect to processing of personal data.

This study will also be carried out in accordance with Organic Law 15/1999, of December 13, on the protection of personal data.

In accordance with the provisions of the aforementioned legislation, patients may exercise the rights of access, modification, opposition and cancellation of data, for which they must contact the clinical trial doctor.

The content of the CRD as well as the documents generated during the study will be considered strictly confidential and will not be revealed to third parties.

12.10. Documentation

The investigator/institution shall maintain the trial documents in accordance with ICH Topic E6 Section 8, and in accordance with relevant regulatory requirements.

Essential documents should be archived in accordance with BPC guidelines or for a longer period of time, if required by relevant regulations.

The original data of study patients (medical records) should be stored according to the archival period applicable at the study centers, but not for a period shorter than 25 years.

ANNEX II - BARTHEL INDEX

Item	Patient Situation	Points
Eat	Totally independent	10
	Need help cutting meat, bread, etc.	5
	Dependent	0
wash up	Independent: enters and leaves the bathroom alone	5
	Dependent	0
Get dressed	Independent: Able to put on and take off clothes, button, tie shoes	10
	Need help	5
	Dependent	0
To get ready	Independent for washing your face, hands, combing your hair, shaving, putting on makeup, etc.	5
	Dependent	0
Depositions (assess the previous week)	Normal continence	10
	Occasionally an episode of incontinence, or need help administering suppositories or lavatinas	5
	Incontinence	0
Urination (assess the previous week)	Normal continence, or able to care for the catheter if it is inserted	10
	At most one episode of incontinence per day, or needs help caring for the catheter	5
	Incontinence	0
Use the toilet	Independent to go to the toilet room, take off and put on clothes	10
	He needs help to go to the toilet but he cleans himself	5
	Dependent	0
Move	Independent to go from the chair to the bed	15
	Minimal physical help or supervision to do it	10
	Needs a lot of help, but is able to sit alone	5
	Dependent	0
Wander	Independent, walks only a distance of 50 meters	15
	Needs physical assistance or supervision to walk a distance of 50 meters	10
	Independent in a wheelchair without assistance	5
	Dependent	0
Steps	Independent for going down and up stairs	10
	Need physical help or supervision to do it	5
	Dependent	0

Total:

Maximum score: 100 points (90 if you are in a wheelchair)

Result and degree of dependency

<20	Total
20-35	Grave
40-55	Moderate
>= 60	Light
100	Independent

ANNEX III - MINI MENTAL STATE EXAMINATION (MMSE) - Adapted ESPAÑA

**MINI MENTAL STATE EXAMINATION
(MMSE)**

Basado en Folstein et al. (1975), Lobo et al. (1979)

Nombre: _____ Varón [] Mujer []
 Fecha: _____ F. nacimiento: _____ Edad: _____
 Estudios/Profesión: _____ N. Hª: _____
 Observaciones: _____

¿En qué año estamos? 0-1 ¿En qué estación? 0-1 ¿En qué día (fecha)? 0-1 ¿En qué mes? 0-1 ¿En qué día de la semana? 0-1		ORIENTACIÓN TEMPORAL (Máx.5)	
¿En qué hospital (o lugar) estamos? 0-1 ¿En qué piso (o planta, sala, servicio)? 0-1 ¿En qué pueblo (ciudad)? 0-1 ¿En qué provincia estamos? 0-1 ¿En qué país (o nación, autonomía)? 0-1		ORIENTACIÓN ESPACIAL (Máx.5)	
Nombre tres palabras Peseta-Caballo-Manzana (o Balón-Bandera-Árbol) a razón de 1 por segundo. Luego se pide al paciente que las repita. Esta primera repetición otorga la puntuación. Otorgue 1 punto por cada palabra correcta, pero continúe diciéndolas hasta que el sujeto repita las 3, hasta un máximo de 6 veces. Peseta 0-1 Caballo 0-1 Manzana 0-1 (Balón 0-1 Bandera 0-1 Árbol 0-1)		Nº de repeticiones necesarias FIJACIÓN-Recuerdo Inmediato (Máx.3)	
Si tiene 30 pesetas y me va dando de tres en tres, ¿Cuántas le van quedando?. Detenga la prueba tras 5 sustracciones. Si el sujeto no puede realizar esta prueba, pídale que deletree la palabra MUNDO al revés. 30 0-1 27 0-1 24 0-1 21 0-1 18 0-1 (0 0-1 D 0-1 N 0-1 U 0-1 M0-1)		ATENCIÓN-CÁLCULO (Máx.5)	
Preguntar por las tres palabras mencionadas anteriormente. Peseta 0-1 Caballo 0-1 Manzana 0-1 (Balón 0-1 Bandera 0-1 Árbol 0-1)		RECUERDO diferido (Máx.3)	
DENOMINACIÓN. Mostrarle un lápiz o un bolígrafo y preguntar ¿qué es esto?. Hacer lo mismo con un reloj de pulsera. Lápiz 0-1 Reloj 0-1 REPETICIÓN. Pedirle que repita la frase: "ni sí, ni no, ni pero" (o "En un trigal había 5 perros") 0-1 ÓRDENES. Pedirle que siga la orden: "coja un papel con la mano derecha, dóblelo por la mitad, y póngalo en el suelo". Coje con mano d. 0-1 dobla por mitad 0-1 pone en suelo 0-1 LECTURA. Escriba legiblemente en un papel "Cierre los ojos". Pídale que lo lea y haga lo que dice la frase 0-1 ESCRITURA. Que escriba una frase (con sujeto y predicado) 0-1 COPIA. Dibuje 2 pentágonos interseccionados y pida al sujeto que los copie tal cual. Para otorgar un punto deben estar presentes los 10 ángulos y la intersección. 0-1		LENGUAJE (Máx.9)	
Puntuaciones de referencia 27 ó más: normal 24 ó menos: sospecha patológica 12-24: deterioro 9-12 : demencia		Puntuación Total (Máx.: 30 puntos)	

a.e.g.(1999)

ANNEX IV - RANO RESPONSE CRITERIA

	RC	RP	EE	PROGRESIÓN
T1-GD	0	≥50% ↓	>50% ↓ <25 %↑	≥ 25 % ↑*
T2/FLAIR	=, ↓	=, ↓	=, ↓	=, ↑*
NUEVAS LESIONES	0	0	0	0. +*
CORTICOSTERIOIDES	0	=, ↓	=, ↓	=, ↑*
CLÍNICA	=, ↑	=, ↑	=, ↑	=, ↓*
	todas	todas	todas	Cualquiera *

COMPLETE ANSWER:

Disappearance of signal in T1Gd MRI
 Stability or reduction in Flair/T2 images
 No new radiological lesions
 Stability or clinical improvement
 Absence of corticosteroids or minimum stable dose

PARTIAL ANSWER:

MRI image reduction by 50% in T1Gd
 Stability or reduction in Flair/T2 images
 No new radiological lesions
 Stability or clinical improvement
 With reduced or stable steroids

PROGRESSION: Any of the following

25% growth of the tumor in T1Gd MRI
 Significant increase in Flair/T2 images*
 Appearance of new lesions
 Irreversible clinical neurological worsening, even in the absence of radiological worsening.
 Need to increase dexamethasone (>2 weeks) to prevent progressive neurological deterioration.
USE: Only progression criteria 1,2 and 3 are applicable for the purposes of patient inclusion in the clinical trial.

STABLE DISEASE:

T1Gd image with an increase of less than 25% or a decrease of less than 50%
 Flair/T2 Image Stability
 No new radiological lesions
 clinically stable
 Stable cortisone doses (which should not be increased to maintain neurological deterioration)

*not attributable to radiotherapy, demyelination, ischemia, infection, seizures, postoperative changes or other treatment effects.

1. RESULTS (TABLES, LISTS AND FIGURES)

The database of the study was closed on the 10-10-2019.

1.1. STUDY POPULATION

1.1.1. SCREENED PATIENTS

A total of xx patients were screened and eventually xx patients fulfilled all the inclusion and exclusion criteria.

Table 1. Screened patients

		N	%
Hospital	Name		
	Total		
Fulfills every inclusion and none of the exclusion criteria	Patient fulfils all the inclusion criteria and none of exclusion according to the protocol		
	Patient does not fulfil the eligibility criteria		
	Total		

xx patients were considered evaluable for the study and the reason for non-evaluability was screening failure in all the cases.

Table 2. Evaluable patients

		N	%
Evaluable patients	No		
	Yes		
	Total		
Non evaluable reason	Screening failure		
	Total		

Table 3. Patients included and excluded from each hospital

Hospital	Name	Evaluable patients					
		No		Yes		Total	
		N	%	N	%	N	%
						

Those patients excluded from the analysis are listed in the following table.

Table 4. List of patients excluded from the analysis

Patient number	Hospital	Non evaluable reason	Fulfils every inclusion and none of the exclusion criteria
1			
2			
3			
4			
..			

DEMOGRAPHIC AND CLINICAL BASELINE CHARACTERISTICS

The median of the age was xx years and xx % were males.

Table 5. Age

	N	Mean	SD	Median	Min	Max
Age in years (at informed consent signature)						

Table 6. Gender and race

	N	%
Gender	Men	
	Female	
	Total	
Race	White	
	Hispanic	
	Total	

1.1.2. CLINICAL BASELINE CHARACTERISTICS**Table 7. Clinical data**

	N	%
Performance Status (PS)	0	
	1	
	2	
Total		

	N	Mean	SD	Median	Min	Max
Systolic blood pressure						
Diastolic blood pressure						
Weight						
Height						

Table 8. Analytical data

	N	Mean	SD	Median	Min	Max
Haemoglobin (g/dl)						
Platelets (x 10e9/L)						
Leukocytes (x 10e9/L)						
Neutrophils (x 10e9/L)						
Lymphocytes (x 10e9/L)						

Table 9. Biochemistry data

	N	Mean	SD	Median	Min	Max
Sodium (mmol/L)						
Potassium (mmol/L)						
Calcium (mg/dL)						
Magnesium (mg/dL)						
Glucose (mg/dL)						
Creatinine (mg/dL)						
AST (U/L)						
ALT (U/L)						
Total bilirubin (mg/dL)						
GGT (U/L)						
Alkaline Phosphatase (U/L)						
Albumin (g/dL)						
LDH (U/L)						

Table 10. Coagulation data

	N	Mean	SD	Median	Min	Max
TP value						
TTPA value						
Fib (mg/dL)						

Table 11. Thyroid function

	N	Mean	SD	Median	Min	Max
TSH value						
T3 value						

Table 12. ECG

	N	%
Qtc	Unknown	
	<450 mseg	
	450-480 mseg	
	Total	

1.1.3. CLINICAL TUMOUR CHARACTERISTICS

In the first surgery 16 patients (47.1%) had a tumour of grade 2 while 13 (38.2%) had a grade 3 tumour.

Table 13. First surgery characteristics

	N	%
Diagnosis with grade (First surgery)	Oligoastrocytoma grade 2	
	Oligoastrocytoma grade 3	
	Oligodendroglioma grade 2	
	Oligodendroglioma grade 3	
	Oligodendroglioma grade unknown	
	Diagnosis and grade unknown	
	Total	
Grade (First surgery)	Grade 2	
	Grade 3	
	Unknown	
	Total	
Anaplasia (First surgery)	0	
	1	
	2	
	4	
	Unknown	
	Total	
High cellularity (First surgery)	No	
	Yes	
	Total	
Endothelial proliferation (First surgery)	No	
	Yes	
	Total	
Necrosis (First surgery)	No	
	Yes	
	Total	
Mitosis (First surgery)	No	
	Yes	
	Total	
Nuclear anomalies (First surgery)	No	
	Yes	
	Total	

Table 14. List of patients with diagnosis in first surgery

Patient number	Hospital	Diagnosis with grade (First surgery)	Grade (First surgery)
1			
2			
3			
4			
5			
...			

In the last surgery, every patient (100%) was diagnosed with an oligodendroglioma grade 3.

Table 15. Last surgery characteristics

	N	%
Diagnosis with grade (Last surgery)	Oligodendroglioma grade 3	
	Total	
Grade (Last surgery)	Grade 3	
	Total	
Anaplasia (Last surgery)	0	
	1	
	2	
	3	
	4	
	5	
	Total	
High cellularity (Last surgery)	No	
	Yes	
	Total	
Endothelial proliferation (Last surgery)	No	
	Yes	
	Total	
Necrosis (Last surgery)	No	
	Yes	
	Total	
Mitosis (Last surgery)	No	
	Yes	
	Total	
Nuclear anomalies (Last surgery)	No	
	Yes	
	Total	

Table 16. Deletion

	N	%
Deletion 1p	Yes	
	Total	
Deletion 19q	Yes	
	Total	

In x patients (xx%) the surgery was not completed. Biopsy was performed in x patients (xx%) and craniotomy in XX patients (xx%).

Table 17. Surgery compliance

		N	%
Surgery	No		
	Yes		
	Total		
Type of surgery	Biopsy		
	Craniotomy		
	No applicable (Surgery not done)		
	Total		
Relapse location	Bihemispheric		
	Cingulate (right)		
 (Indicate locations)		
	Total		

The baseline barthel index mean was xx and the baseline minimal test mean was xx (data was available in xx patients).

Table 18. Baseline Barthel Index and Minimal test

	N	Mean	SD	Median	Min	Max
Barthel index (baseline)						
Mini mental test (baseline)						

1.2.3. PREVIOUS PATHOLOGIES

For 9 patients (26.5%) previous pathologies were not reported. In those patients with previous pathologies, seizures were the most common (n=7, 17.6%) previous pathology.

Table 19. Previous pathologies

		N	%
Previous pathologies	No		
	Yes		
	Total		
Previous pathologies	(Indicate previous pathologies. Exemples:		
	Fatigue		
	Cognitive disturbance		
	Muscle weakness left-sided		
		

Table 20. List of previous pathologies

Pat. n.	Hospital	Previous pathology	Intensity	Action
1	01-003			
2	01-004			
3	01-006			
..	01-006			

Table 21. Time since diagnosis

	N	Mean	SD	Median	Min	Max
Time since 1st diagnosis until 1st cycle (months)						

1.2. EFFICACY ANALYSES

1.2.1. PRIMARY EFFICACY ANALYSES: PFS

At 6 and 9 months the estimated PFS was 21.23% (with 95% CI 11-40.97), at 12 months it was 16.99% (with 95% CI 7.71-37.43) and from 18 to 48 months it was 11.32% (with 95% CI 3.68-34.86).

The median of PFS was 2.84 months (with 95% CI 2.71-5.39).

Table 22. PFS estimated survival ratio

Progression Free Survival	Events (% total N)	Patients at risk	% estimated cumulative survival ratio	CI 95%
At 6 months				
At 9 months				
At 12 months				
At 18 months				
At 24 months				
At 30 months				
At 36 months				
At 42 months				
At 48 months				

[figure not shown]
Note: Estimated using Kaplan-Meier product-limit method

Table 23. Median/mean PFS (estimated by Kaplan-Meier)

Progression Free Survival	Median (months)	CI 95%	Mean	CI 95%

Note: Estimated using Kaplan-Meier product-limit method

Figure 1. Progression Free Survival

In the 28 patients with PD, the median until progression was 2.8 months.

Table 24. Time until PD/exitus (only pts with event)

Overall	Overall (N=xx)
Time until PD/Exitus	
N	
Mean (95%CI)	
SD	
Median (95%CI)	
Range	

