10.3. Hypothesis

Clinical basis: historical data for the elaboration of the study hypothesis have been obtained from the analysis of a database containing 350 patients with recurrent high-grade gliomas (125 anaplastic gliomas) who were prospectively treated in phase II studies. The 6-month progression-free survival (PFS-6m) was 31% for anaplastic gliomas (Wong et al. J Clin Oncol 17:2572-2578). The authors acknowledge the limitation because in this study the results were analyzed for all anaplastic gliomas and not only anaplastic oligodendrogliomas. However, no further published data are available regarding the results in recurrent anaplastic oligodendrogliomas.

Null hypothesis (H0): $P \leq P_0$

Alternative hypothesis to test (H1): $P \geq P_1$

Assumptions:

P: probability of remaining alive and progression-free at 6 months

P_0 : 25%

P_1 : 45%

Expected profit: 20% (25% vs. 45%)

Type I error, $\alpha \leq 0.05$

Type II error, $\beta \geq 0.20$

Sample size: 40 patients

A benefit will be considered if 18/40 patients are alive and progression-free at 6 months.

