10.4. Statistic analysis

Associations between overall survival and progression-free survival with patients' baseline characteristics will be evaluated using the log-rank test.

The maximum relative risk value based on the log-rank test will be used to provide a quantitative summary of the data, with 95% confidence intervals. Median survival, time to progression, and associated 95% confidence intervals will be calculated. Kaplan-Meier curves will be constructed to show the estimated probabilities of overall survival and time to progression.

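### The 18/40 success rule in protocol 10.3 has about 56% power at the 45% target, not the 80% evidently intended, and neither protocol 10.4 nor SAP 1.2.1 applies it, or any comparison with 25%, to the 34 patients analysed

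*SAP*

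**What the plan says.** Protocol 10.3 defines P as the probability of being alive and without progression at 6 months, with H0: P ≤ P0 and H1: P ≥ P1. The design difference is "Expected profit: 20% (25% vs. 45"%). Alpha is printed as ≤ 0.05 with no sidedness, beta as ≥ 0.20, and the sample size as 40. The success rule is "A benefit will be considered if 18/40 patients are alive and progression-free at 6 months". The same section gives its historical basis: "The 6-month progression-free survival (PFS-6m) was 31% for anaplastic gliomas". It then uses 25% as the null and gives no reason for the lower figure.

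Protocol 10.4 lists log-rank associations with baseline characteristics, medians with confidence intervals, and curves: "Kaplan-Meier curves will be constructed to show the estimated probabilities of overall survival and time to progression". It contains no test of P against P0.

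SAP 1.2.1 is the primary efficacy analysis. It prints "At 6 and 9 months the estimated PFS was 21.23% (with 95% CI 11-40.97"), and plans "Table 22. PFS estimated survival ratio", with columns for events and patients at risk at each time. It mentions neither 18/40, nor 25%, nor 45%. The number analysed appears elsewhere in the SAP: the adverse event table footnote uses N=34, and Table 53 has columns of 27, 7 and 34. On exclusions, SAP 1.1.1 says "the reason for non-evaluability was screening failure in all the cases". On timing, section 1 says "The database of the study was closed on the 10-10-2019".

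**The concern.** A single-arm phase II trial rests on its decision rule, and here two things go wrong with it. The cut-off equals the target rate, so a drug that truly reaches 45% passes only slightly more than half the time. And the primary analysis never uses the rule, so the report would not answer the hypothesis in protocol 10.3. With 34 patients instead of 40, a reader cannot tell whether 18, a proportional cut-off or a recalculated one applies. The null matters as well, because a cut-off that controls error at 25% may not do so at the cited 31%. A negative pilot is read differently if its rule had 56% power and not 80%.

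**Working it through.** **Inputs.** P0=0.25, P1=0.45, alpha 0.05, N=40, cut-off 18 and historical rate 0.31 (protocol 10.3). N=34 and 7 patients with PFS of at least 9 months (SAP Table 53); 28 patients with PD and the printed PFS rates (SAP 1.2.1). Beta is taken as 0.20.

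**1. The planned N.** n = [z_α√(P0(1−P0)) + z_0.80√(P1(1−P1))]² / (P1−P0)².
- One-sided 0.05: (1.645×0.4330 + 0.8416×0.4975)² / 0.04 = 31.98.
- Two-sided 0.05: (1.960×0.4330 + 0.8416×0.4975)² / 0.04 = 40.16.

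The smallest exact one-sided design with 80% power is 14/36 (alpha 0.046, power 0.82). So 40 is reasonable for 80% power, which supports reading beta as 0.20.

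**2. The cut-off.** The tail is P(X ≥ r) for X ~ Binomial(n, p), at p = 0.25 (alpha), 0.31 and 0.45 (power).

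| Rule | Tail at 25% | Tail at 31% | Power at 45% |
|---|---|---|---|
| 18/40 (protocol) | 0.0047 | 0.044 | 0.56 |
| 17/40 | 0.012 | 0.083 | 0.68 |
| 16/40 | 0.026 | 0.145 | 0.79 |
| 15/40 | 0.054 | 0.233 | 0.87 |

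Since 18 = 0.45×40, the rule asks the observed rate to reach P1. The lowest cut-off that holds one-sided 0.05 against 25% is 16, with power 79%. For two-sided 0.05 (upper tail 0.025) it is 17.

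**3. Carrying the rule to 34.**

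| Rule | Tail at 25% | Tail at 31% | Power at 45% |
|---|---|---|---|
| 14/34 | 0.028 | 0.137 | 0.73 |
| 15/34 | 0.012 | 0.074 | 0.61 |
| 16/34 | 0.0044 | 0.036 | 0.47 |
| 18/34 | 0.0004 | 0.006 | 0.22 |

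16/34 is the proportional carry-over (0.45×34 = 15.3, rounded up). It has nearly the same alpha as 18/40, and it is the lowest of these cut-offs that holds 0.05 against 31%.

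**4. The count behind 21.23%.** Start with 34 patients. After one event and then one censoring, 32 remain at risk; 25 more events leave 7. The estimate is (33/34)×(7/32) = 0.2123. Adding events with 5 and 3 at risk gives 0.2123×4/5 = 0.1699 and 0.1699×2/3 = 0.1132. Log-transformed Greenwood limits are 11.00–40.97, 7.71–37.43 and 3.68–34.86, matching all the printed PFS rates and limits from 6 to 48 months. Total events are 26+2 = 28, as printed, and the 7 match Table 53. The one early-censored patient is the only possible eighth success.

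**5. Result against 25%.**
- 7/34: upper-tail p = 0.78; Clopper-Pearson 90% interval 10.1–35.2%.
- 8/34: p = 0.64; 90% interval 12.3–38.5%.

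Even six further patients, all successes, would give at most 14/40 (p = 0.10), short of 16, 17 and 18.

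**The case against.** The strongest reply is that nothing of consequence changes. The printed interval includes 25% and excludes 45%, the database is closed, and the trial is a pilot. That stands for the conclusion. It does not supply the missing answer to the stated hypothesis, and it does not correct the power that a reader would assume.

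A second reply is that 18/40 may be a bar for worthwhile benefit and not the rejection point of a test. The documents do not settle this. It is still the only success rule stated, and the primary analysis does not use it.

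Third, the rule already stands in protocol 10.3, so 10.4 need not repeat it, and Table 22 could yield a count. This is partly right: the rule is unlinked, not absent. But nothing directs the analyst to make the comparison, and nothing covers N=34.

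Some stronger readings are tempting. A reader might infer that 18/40 breaches the printed error rates. Taken literally it does not, because 0.0047 is below 0.05 and a beta of 0.44 is above 0.20. A reader might infer that 40 was too few, but step 1 shows otherwise. A reader might infer that 18 was derived from the 31% null, since it holds one-sided 0.05 there (0.044). The protocol does not say so, and power at 45% would still be 56%. Nor do the documents show that six treated patients were dropped, since screening failure is the only reason given for non-evaluability.

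**Conclusion.** The point holds as a fault in the cut-off and in its link to the analysis. With 18/40, a true 45% rate is missed 44% of the time, where 20% was evidently intended. The rule is not applied in protocol 10.4 or SAP 1.2.1, and the choice of cut-off for 34 patients moves power between 0.22 and 0.73. The unexplained step from 31% to 25% adds to the ambiguity: at a true 31%, 14/34 would be reached 13.7% of the time and 16/34 only 3.6%.

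This should be corrected in the report, but it does not alter the outcome: 7 or 8 of 34 fails every reading.

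Three assumptions carry the verdict: beta was meant as 0.20, 18 is the threshold for declaring success, and 34 is the number treated. The directional hypotheses point to a one-sided alpha. Two-sided 0.05 comes close to N=40 by the normal formula (40.16, or 41 rounded up), but that alone does not make the test two-sided.

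**What to change.** 1. In the account of protocol 10.3, restate the power of 18/40 as about 56%, correct the beta sign and state that alpha is one-sided. Give 16/40 (0.026, 79%) as the cut-off that matches the design. Show 17/40 (0.012, 68%) only as a sensitivity reading for two-sided 0.05.
2. In SAP 1.2.1, report the number alive and progression-free at 6 months among all treated patients against the prespecified 18/40. Add an exact binomial test against 25% and a Clopper-Pearson interval (90% for one-sided 0.05). Count unknown status as failure, and show the early-censored patient both ways (7/34 and 8/34).
3. If cut-offs for 34 are shown, list 14, 15 and 16 with their tails at 25% and 31% and their power, as tabulated above.
4. Label the exact test, the interval level, the unknown-as-failure rule and every 34-patient cut-off as post hoc, because this SAP already prints results.
5. State that the cited historical rate is 31%, say that no reason is given for using 25%, and report the 18/40 tail at 31% (0.044).
6. Keep the Kaplan-Meier estimate as supportive and name its interval method.

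The cost is wording and a few lines of code, with no new data. The downside is that the report must say that power was below 80% and that these additions came after the results.
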